11.2.3.4 Metastasis-Free Survival and Time to Metastases

The duration of MFS, defined as the time from first dose of VTP-850 to detection of metastatic disease or all-cause mortality, will be summarised (n, median, interquartile range, minimum, maximum) and presented using a Kaplan-Meier plot. Participants who have survived without development of metastatic disease by the end of follow-up will be censored at the time of their last follow-up visit with an evaluable assessment of metastatic disease.

The duration of TTM, defined as the time from first dose of VTP-850 to detection of metastatic disease, will be summarised (n, median, interquartile range, minimum, maximum) and presented using a Kaplan-Meier plot. Participants who have not developed metastatic disease by the end of follow-up will be censored at the time of their last follow-up visit with an evaluable assessment of metastatic disease.

These endpoints will be further summarised by whether the participants had prior radical prostatectomy, external beam radiation or brachytherapy. These endpoints will be further summarised for participants who experienced a PSA response.

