|----------------------|--|--|
| | 
To assess the MFS and TTM of all participants
 | 
 • MFS is defined as the time from date of first dose of VTP-850 until metastatic disease by conventional imaging (CT/MRI and/or technetium-99 bone scan) or death from any cause, whichever occurs first • TTM is defined as the time from date of first dose of VTP-850 until metastatic disease by conventional imaging (CT/MRI and/or technetium-99 bone scan) 
Note that MFS and TTM events do not include local progression events, e.g., progression in pelvic lymph nodes below the aortic bifurcation
 |

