| Immunogenicity assessments | | | | | | | | |
| Blood for PBMC assessment ^f | | | | | X | X | | |
| Blood for anti-antigen antibody assessment | | | | | X | X | | |

Abbreviations: AESIs- Adverse Events of Special Interest, d=days, EOT=End of Trial, PBMC=peripheral blood mononuclear cells, PSA=prostate-specific antigen, PSMA=prostate-specific membrane antigen

^a Participants will only have 1 EOT visit at either Months 6 or 24 or earlier in the event of initiation of new therapy (such as ADT) or development of unequivocal metastatic prostate cancer. Participants with no PSA response in the first 6 months will not enter the Long-Term Follow-up Period. Participants with a PSA response through Month 6 will enter the Long-term Follow-up Period.

^b Visits during the Follow-up Periods are from Day 1. Windows are relative to the target date of the visit.

^c If a cardiac event is reported, blood should be taken for an additional assessment of troponin T and the participant should undergo an additional ECG and echocardiogram at the earliest opportunity

^d If troponin T test result is abnormal, a re-test on the following day is required.

^e PSMA scan can be performed at any time for participants who had a positive PSMA scan prior to screening and where a 50% reduction from baseline in PSA is observed.

^fOnly required at sites qualified by Barinthus Biotherapeutics to perform PBMC isolation/processing.

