3 OBJECTIVES AND ENDPOINTS

| Primary Objective | Primary Endpoints |
|--|---|
| To evaluate the safety of VTP-850 prime-boost regimens, with the booster dose administered either IM or IV, and establish an RP2R | 
 Number and proportion of participants with AEs, treatment-related AEs, \geGrade 3 AEs, \geGrade 3 treatment-related AEs, serious adverse events, and treatment-related serious adverse events Number and proportion of participants with clinically significant laboratory values Change from baseline for laboratory tests and vital sign measurements at each time point of collection |
| Secondary Objectives | Secondary Endpoints |
| To evaluate the PSA response rate to VTP-850 | 
 Percentage of participants with \ge50% reduction in serum PSA compared to baseline at any time, based on two consecutive measurements, at least 2 weeks apart |
| To evaluate the durable PSA response rate to VTP-850 | 
 Percentage of participants with confirmed PSA response compared to baseline without having PSA progression on or before Month 8. |
| To evaluate the duration of PSA response to VTP-850 (for the subset of participants with PSA response) | 
 Duration of PSA response (for the subset of participants with PSA response), defined as time from date of first dose of VTP-850 to the date of PSA progression (i.e., an increase of \ge25% and an absolute increase of 0.2 ng/mL or more from nadir) |
| To assess the Metastasis-free Survival (MFS) and Time to Metastases (TTM) of the subset of participants with PSA response | 
 MFS is defined as the time from date of first dose of VTP-850 until metastatic disease by conventional imaging (CT/MRI and/or technetium-99 bone scan) or death from any cause, whichever occurs first TTM is defined as the time from date of first dose of VTP-850 until metastatic disease by conventional imaging (CT/MRI and/or technetium-99 bone scan) 
Note that MFS and TTM events do not include local progression events, e.g., progression in pelvic lymph nodes below the aortic bifurcation.
 |
| To assess the time to start of ADT for the participants with PSA response | 
 Time from date of first dose of VTP-850 to the earliest of the start of ADT or the date when criteria to start ADT are met |
| Exploratory Objectives | Exploratory Endpoints |

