4.1.4 Duration of Trial for Participants

The trial consists of the following periods:

- Screening Period: Up to 42 days from informed consent until VTP-850 prime dose.
- Intervention Period: From VTP-850 prime dose until the Day 91 Clinic Visit.

Short-term Follow-up Period: All participants will be followed monthly from the end of the intervention period until the Month 6 Visit or until start of new therapy such as ADT or development of unequivocal metastatic prostate cancer, if sooner. If a participant does not have a PSA response by their Month 6 visit, they will complete their EoT visit and will not enter the Long-term Follow-up Period.

Long-term Follow-up Period: Participants who have PSA response will be followed for an additional 18 months, up to 24 months from first dose, or until start of new therapy such as ADT or development of unequivocal metastatic prostate cancer, if sooner. Clinic visits will be monthly to Month 12 and bimonthly thereafter. If a participant has a significant decrease in PSA but does not meet the criteria for a PSA responder e.g., the confirmatory measurement is not yet performed, discuss with the Medical Monitor whether the participant should continue follow-up.

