6.12 Delay to Dosing Due to Study Pause

Participants whose scheduled dosing of MVA-PCAQ is delayed due to a study pause during the Phase 1 portion of the study will be offered to recommence dosing and follow the SoA from Day 57. These participants will also be replaced to ensure that 6 participants are dosed in each of Cohorts 2 and 3, to allow for a meaningful assessment at the end of Phase 1.

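### After Month 6 the all-participant MFS and TTM curves rest essentially on PSA responders, because nearly all non-responders are censored by then

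*Protocol*

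**What the plan says.** Protocol 11.2.3.4 summarises MFS and TTM by n, median, interquartile range, minimum and maximum, with a Kaplan-Meier plot. For MFS, "Participants who have survived without development of metastatic disease by the end of follow-up will be censored at the time of their last follow-up visit"; the sentence goes on to require that metastasis was evaluable at that visit. TTM has a parallel rule. Neither has an upper time limit. Responders come in only as an addition: "These endpoints will be further summarised for participants who experienced a PSA response". The base curve is therefore for everyone, which matches the exploratory objective in the Synopsis and Section 3: "To assess the MFS and TTM of all participants". The clock starts at first dose: "MFS is defined as the time from date of first dose of VTP-850 until metastatic disease by conventional imaging", or death in the case of MFS.

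Follow-up, however, depends on PSA response. Table 2, footnote a: "Participants with no PSA response in the first 6 months will not enter the Long-Term Follow-up Period". Section 4.1.4: "If a participant does not have a PSA response by their Month 6 visit, they will complete their EoT visit", and they do not go on to long-term follow-up. Responders can be followed to Month 24 (Section 4.1). Table 2 schedules on-study imaging at Months 6, 12, 18 and 24, each within 14 days either side.

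There are two exceptions, and no number is given for either. For a marked PSA fall that does not yet qualify as a response, the site is to "discuss with the Medical Monitor whether the participant should continue follow-up" (4.1.4). Phase 1 participants whose MVA-PCAQ dosing was delayed by the study pause "will be offered to recommence dosing and follow the SoA from Day 57" (6.12).

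The current SAP covers Phase 1 only. It assigns the MFS and TTM objectives to Phase 2 (SAP 2.2.2 and 2.2.3) and leaves Phase 2 to a later SAP (SAP 2.1).

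**The concern.** Kaplan-Meier estimation treats people censored at a given time as having the same later risk as those still under observation. Here PSA response decides who stays under observation. A non-responder normally contributes one on-study scan, at Month 6, and is then censored. From that point the all-participant curve multiplies everyone's survival to Month 6 by the responders' survival after Month 6.

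That product estimates all-participant MFS only if PSA response is unrelated to later metastasis or death. The protocol does not say so, and following responders for metastases (Section 2.1) treats the relation as an open question. A curve labelled as all participants and running to Month 24 would be read as the experience of the whole population while carrying almost no information on about four fifths of it. TTM has the same problem.

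**Working it through.** **The plan's own figures.** The documents state no MFS or TTM rate. The 20% response rate used below comes from Protocol 11.4, and the calculations there reproduce by exact binomial: at least 4 of 25 at 20% has probability 0.7660 (stated 76.6%); at least 20 of 125 has probability 0.8932 at 20% (stated 89.3%).

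**Who leaves at Month 6.** At 20% response, 25 of 125 participants are responders and 100 are not. If responder 24-month MFS is 90% (assumed), the fraction event-free at Month 6 is 0.9^(6/24) = 0.974. The number at risk just after Month 6 is then 125 × 0.20 × 0.974 ≈ 24. At 10% and 30% response it is about 12 and 37. With all 144 planned participants it is 144 × 0.20 × 0.974 ≈ 28.

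**What the curve estimates.** Let p be the response rate and SR and SN the 24-month MFS in responders and non-responders, with exponential times and hazards hR = −ln(SR)/24 and hN = −ln(SN)/24.

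- True value: p·SR + (1 − p)·SN
- Planned curve at 24 months: [p·exp(−6hR) + (1 − p)·exp(−6hN)] × exp(−18hR)

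For p = 0.20, SR = 0.90, SN = 0.70:

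- True value: 0.2 × 0.90 + 0.8 × 0.70 = 0.740
- Curve at Month 6: 0.2 × 0.9740 + 0.8 × 0.9147 = 0.9266
- Curve at Month 24: 0.9266 × 0.9^(18/24) = 0.9266 × 0.9240 = 0.856
- Difference: +11.6 points

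**Range.** SR and SN are assumptions throughout.

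| Scenario | True | Curve | Bias (points) |
|---|---|---|---|
| p = 0.20, SR 0.90, SN 0.70 | 74.0% | 85.6% | +11.6 |
| p = 0.10, SR 0.90, SN 0.60 (grid maximum) | 63.0% | 82.2% | +19.2 |
| SR = SN = 0.80 (grid minimum) | 80.0% | 80.0% | 0 |
| p = 0.20, SR 0.70, SN 0.80 (responders worse) | 78.0% | 71.9% | −6.1 |

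The grid is p = 0.10, 0.20, 0.30; SR = 0.80, 0.85, 0.90; SN = 0.60, 0.70, 0.80. The curve at 24 months lies between 75.0% and 88.2% in all 27 cells, so no median is reached.

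**Simulation.** With 125 participants, scans at Months 6, 12, 18 and 24, 20% response, SN = 0.70 and a responder hazard ratio of 0.5, the mean 24-month curve was 0.808 against a true 0.728 (formula: 0.807 and 0.727). On average 23.9 people were at risk at the Month 12 scan, all responders. At a hazard ratio of 1 the values were 0.698 and 0.699.

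**Precision at equal risk.** With 24-month MFS of 70% in both groups there is no bias. Event-free fractions are 0.7^(6/24) = 0.9147 to Month 6 and 0.7^(18/24) = 0.7653 from Month 6 to Month 24, and 25 × 0.9147 ≈ 22.9 responders remain at risk after Month 6.

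- Planned follow-up: SE = 0.7 × √[0.0853/(0.9147 × 125) + 0.2347/(0.7653 × 22.9)] = 0.083
- Full follow-up of all 125: SE = √(0.7 × 0.3/125) = 0.041

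**The exceptions.** About 25 are to be enrolled in Phase 1 against 15 to 18 cohort places, leaving 7 to 10 extra. Suppose all of these were pause-delayed non-responders kept past Month 6. Of 0.8 × 144 ≈ 115 non-responders, 91% (1 − 10/115.2) to 94% (1 − 7/115.2) would still be censored by then. The 28.8 expected responders would be 74% to 80% of the early post-Month 6 risk set. At 10% response (14.4 responders) they would be 59% to 67%.

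**The case against.** The strongest reply is that this is early and minor. The all-participant objective is exploratory, Protocol 11.2.4 leaves exploratory analyses to the SAP, and 11.2.3.4 sits among the secondary analyses, where the objective concerns responders only. All of that is true, and the responder-only endpoint is untouched by this point. But 11.2.3.4 is the only description of the method, it adds responders to an all-participant base, and nothing in it would stop the problem from passing into the Phase 2 SAP.

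Second, the plan reports medians and quartiles, not a 24-month rate, and in the grid the median is never reached. That stands: there the harm is in the plotted curve. Quartiles are not always safe, however. With non-responder MFS of 50%, hazard ratio 0.5 and 20% response, the curve is at 0.2 × 0.917 + 0.8 × 0.841 = 0.856 at Month 6 and 0.660 at Month 24, so the 75% point is read from the responder-driven part.

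Third, the grid never lets responders do worse, so it cannot show a negative bias. That is fair; the −6.1 point case is given for that reason, and all sizes are illustrations.

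Fourth, the objective covers about 144 people, not 125, and pause-delayed participants would stay longer. Using 144 moves the number at risk from about 24 to about 28. Under the extreme allocation above, non-responders would have a visible share of the risk set early after Month 6, so the accurate wording is nearly all non-responders, not every one.

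Finally, assigning scans to the nominal visit departs from dating a metastasis when it is seen (8.2.3), and a first-dose origin for responders keeps event-free time that they needed in order to respond. The first can be confined to the one Month 6 estimate, with deaths keeping their exact dates. The second is why the responder display needs its label and why a landmark analysis is a useful supplement.

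**Conclusion.** The concern holds. Up to the Month 6 scan (about Day 166 to 194) the curve is an all-participant estimate, apart from those who left earlier for new therapy. Beyond it, the curve is the whole group's Month 6 survival carried forward at the responders' hazard.

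The direction and size of the bias depend on how response relates to risk, which the documents do not tell us. Under exponential times it is +11.6 points at 24 months in the central illustration, 0 to +19.2 across the grid, and −6.1 in the reverse case. If risks are equal there is no bias, but the standard error is about 8.3 points where full follow-up would give 4.1. The analysis is exploratory and descriptive. It should be corrected before the Phase 2 SAP is final, but it does not threaten the trial's decisions.

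**What to change.** In the Phase 2 SAP, and in Protocol 11.2.3.4 when it is next amended:

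- Limit the all-participant MFS and TTM estimates to the Month 6 imaging visit. For these estimates assign Month 6 scans (within the 14-day window) to the nominal visit, so that events and censoring share one time point; deaths keep their exact dates.
- Report the Month 6 estimate with its confidence interval, and the number who left earlier for new therapy. Truncation does not remove that censoring.
- Give no all-participant curve, median or quartiles beyond Month 6.
- Show Months 6 to 24 for responders only, from first dose as the protocol defines it, with numbers at risk and a label saying that the display is conditional on PSA response. A Month 6 landmark analysis may be added as supplementary.

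The cost is wording and a shorter figure, with no extra visits or data. Changing the protocol text itself would need the usual amendment approval; the SAP route avoids waiting for that. The 24-month all-participant estimate is given up, but the follow-up scheme cannot support it.

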11.2.3.5 Time to Start of ADT for Participants with PSA Response

Among those participants who experienced a PSA response, the time to initiation of ADT treatment (or when they have met the criteria to initiate ADT) will be summarised (number of participants, median, interquartile range, minimum, maximum) and presented using a Kaplan-Meier plot. Responders who have not started ADT or met the criteria to start ADT by the end of follow-up will be censored at the time of their last follow-up visit.

This endpoint will be further summarised by whether the participants had prior radical prostatectomy or external beam radiation. This endpoint will be further summarised for participants who experienced a PSA response.

11.2.4 Exploratory Endpoint Analyses

Exploratory endpoints and planned analyses will be described in detail within the SAP.

11.2.5 Other Analyses

11.2.5.1 Disposition

Participant disposition (such as the number screened, screen failed, treated, completed, discontinued from treatment and discontinued from trial), including reasons for withdrawal, if applicable, will be summarised descriptively.

11.2.5.2 Protocol Deviations

Protocol deviations will be listed including the nature (e.g., missed procedure(s), early or late procedure(s), missed visits, visit performed out of protocol defined window, prohibited medication taken, trial intervention dosing deviation, inclusion/exclusion criteria deviations, participants not withdrawn but meeting withdrawal criteria, biological sample handling error, other) and major or minor classification.

11.2.5.3 Demographics and Baseline Characteristics

Demographics and baseline characteristics will be listed and summarised descriptively for participants in the safety analysis set.

11.2.5.4 Prior and Concomitant Medications and Procedures

Concomitant medications and procedures will be summarised by Anatomic Therapeutic Chemical classification. Both prior and concomitant medications and procedures will be listed.

11.2.5.5 Medical History

Medical history will be listed, including the verbatim description and associated MedDRA PT and SOC.

11.3 Interim Analysis

Two interim reviews of trial data are planned.

The first is a preliminary assessment of data from the 25 participants who received the RP2R through Stage 1 of Phase 2 to determine whether the trial has provided sufficient evidence of PSA response to warrant enrolment of an additional 100 participants in Phase 2, Stage 2. Enrolment in Stage 2 will begin following the SMC's review of efficacy and safety data after at least 4 PSA responses have occurred among the 25 participants.

In addition to this and other data reviews performed by the SMC (refer to [Section 4.1.1](#)), an interim analysis will be conducted once all participants enrolled in the Phase 2 portion of the trial have been followed through at least the Month 3 visit. The results from this interim analysis will solely be used for the purpose of planning future clinical trials and will not impact the conduct of this trial, i.e., the sample size of the ongoing trial will not expand as a result of this review. Further, given this is an open-label trial without a control arm, and the trial's endpoints will only be evaluated in a descriptive manner upon trial completion, this interim look will not result in a penalty on any pre-planned alpha level. All secondary endpoints described above will be included in the interim analysis.

11.4 Sample Size Determination

A total of approximately 144 participants will be enrolled. A sample size of approximately 125 participants will be eligible for inclusion in the Phase 2 efficacy evaluation.

Twenty-five participants are to be included in the preliminary Stage 1 assessment to expand into Stage 2 of Phase 2 (i.e., the first 19 participants enrolled in Stage 1 and the 6 participants from Phase 1 receiving the RP2R according to the dosing schedule). If the true response rate (where response is defined as $\geq 50\%$ reduction in serum PSA at any 2 consecutive post-baseline timepoints at least 2 weeks apart) associated with VTP-850 administration is $\geq 20\%$, 25 participants will yield a 76.6% chance (i.e., power) of observing 4 or more responders.

One hundred and twenty-five participants (combined Stage 1 enrolment as described above and Stage 2 enrolment in Phase 2) will yield the following 90% and 95% Confidence Intervals (CIs) for the true response rate based on the example observed response rates in Table 6. This Phase 2 sample size has 89.3% power to rule out a null proportion of PSA responders of 10% using a two-sided exact test with a target significance level of 0.05 assuming a true response percentage of 20%. The null hypothesis response rate of 10% will be rejected if at least 20 PSA responders (16%) are observed amongst the 125 participants.

The observed response rate and associated CIs will facilitate decision-making regarding whether to continue the program as well as the appropriate sample size for subsequent trials.

Table 6 Confidence Intervals for True Serum PSA Response Rate Based on Observed Response Rate (n=125)

| Observed Response Rate (%) | 90% Confidence Interval | 95% Confidence Interval |
|----------------------------|-------------------------|-------------------------|
| 0.10 | (0.059, 0.156) | (0.054, 0.166) |
| 0.15 | (0.100, 0.213) | (0.092, 0.225) |
| 0.20 | (0.143, 0.268) | (0.134, 0.281) |
| 0.25 | (0.187, 0.322) | (0.177, 0.335) |
| 0.30 | (0.233, 0.375) | (0.221, 0.388) |

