4.1.2 Phase 2 – Main Phase

Phase 2 of the trial will consist of 2 sequential stages.

In Stage 1 of Phase 2, 19 additional participants will be enrolled at the chosen Phase 2 regimen. If 4 or more of the 25 participants at the RP2R (out of the 19 Phase 2 participants and the 6 Phase 1 participants who received the same dose regimen according to the dosing schedule) have a PSA response, Stage 2 will be opened to enrolment. If 3 or fewer of the 25 participants receiving the RP2R have a PSA response, no further participants will be enrolled. PSA response is defined as $\geq 50\%$ reduction in serum PSA compared to baseline at any time, measured at two consecutive timepoints, at least 2 weeks apart. The decision to open recruitment in Stage 2 will be made by the SMC after reviewing available safety and efficacy data after at least 4 participants have exhibited a PSA response.

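### The 89.3% power in Protocol 11.4 ignores the Stage 1 stop; the two-stage design as written has about 71.5% power at a true 20% PSA response rate

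*Protocol*

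**What the plan says.** Protocol 11.4 gives two probabilities at the same true response rate of 20%.

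- For the Stage 1 assessment: "25 participants will yield a 76.6% chance (i.e., power) of observing 4 or more responders".
- For the full Phase 2 set: "This Phase 2 sample size has 89.3% power to rule out a null proportion of PSA responders of 10% using a two-sided exact test", at a target two-sided significance level of 0.05. The rejection rule follows: "The null hypothesis response rate of 10% will be rejected if at least 20 PSA responders (16%) are observed amongst the 125 participants".

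The 125 are not a fresh sample. Section 11.4 describes them as "One hundred and twenty-five participants (combined Stage 1 enrolment as described above and Stage 2 enrolment in Phase 2"), so the 25 assessed in Stage 1 are among them.

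The stop is worded as binding. Section 4.1.2 says: "If 3 or fewer of the 25 participants receiving the RP2R have a PSA response, no further participants will be enrolled". The synopsis says the same, and 11.3 opens Stage 2 only after at least 4 responses among the 25 and a review by the Safety Monitoring Committee (SMC).

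Neither document gives a power that combines the two rules. SAP 2.3 refers to Protocol 11.4 for the sample size calculation, and the SAP leaves Phase 2 analyses to a separate, future SAP.

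**The concern.** The trial can reach 125 participants, and so 20 responders among 125, only by first recording at least 4 responders among 25. If that first step succeeds 76.6% of the time at a true rate of 20%, the whole sequence cannot succeed 89.3% of the time at that rate. The two figures stand in consecutive paragraphs of 11.4 and contradict each other if both are read as properties of the trial being run.

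What is at stake is planning and interpretation. A reader who takes 89.3% as the power of Phase 2 expects about a 1 in 10 chance that a regimen with a true 20% response rate fails to rule out 10%. Under the design as written that chance is nearly 3 in 10, and most of it comes from stopping at 25 participants. Section 11.4 says the observed rate and its intervals will inform whether the programme continues, so the probability of a false negative is relevant to that decision.

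**Working it through.** **Inputs**

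- Null rate 10%, true rate 20%, two-sided exact test at 0.05 (upper-tail target 0.025): Protocol 11.4.
- Final rule: reject at 20 or more responders of 125: Protocol 11.4.
- Stage 1: 25 participants, stop at 3 or fewer, continue at 4 or more: Protocol 4.1.2 and 11.3.
- Stage 2: 100 further participants, 25 + 100 = 125: Protocol 11.3 and 11.4.

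Let X1 be responders among the first 25, X2 responders among the next 100, and p the true rate.

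**Step 1. Reproduce the stated figures**

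- Single-stage power: P(Bin(125, 0.20) ≥ 20) = 0.8932. The stated 89.3% reproduces.
- Single-stage upper-tail error: P(Bin(125, 0.10) ≥ 20) = 0.0237. A cut-off of 19 would give 0.0428, above 0.025, so 20 is the right boundary for a fixed sample of 125.
- Passing Stage 1: P(Bin(25, 0.20) ≥ 4) = 0.7660. The stated 76.6% reproduces.

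**Step 2. Combine the two rules**

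Overall probability of rejection = Σ over x = 4 to 25 of P(X1 = x) × P(X2 ≥ max(0, 20 − x)), with X1 ~ Bin(25, p) and X2 ~ Bin(100, p).

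- At p = 0.20: 0.7148.
- At p = 0.10: 0.0153.

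**Step 3. Account for the difference**

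The same sum over x = 0 to 3 gives 0.1784 at p = 0.20. These are sequences that would have reached 20 of 125 but are stopped at Stage 1. Check: 0.8932 − 0.1784 = 0.7148.

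**Step 4. Power once Stage 2 has opened**

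0.7148 / 0.7660 = 0.9331. This exceeds 89.3% because the trials that continue already have at least 4 responders.

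**Step 5. Split the probability of failure at a true 20%**

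- Overall: 100 − 71.5 = 28.5%.
- Stopped at Stage 1: 100 − 76.6 = 23.4 points.
- Stage 2 opens but fewer than 20 respond: 76.6 − 71.5 = 5.1 points.

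**Step 6. Other true rates**

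| True rate | Pass Stage 1 | Single-stage, 20 or more of 125 | Two-stage as written |
|---|---|---|---|
| 10% | 23.6% | 2.4% | 1.5% |
| 15% | 52.9% | 41.4% | 29.1% |
| 20% | 76.6% | 89.3% | 71.5% |
| 25% | 90.4% | 99.4% | 90.1% |
| 30% | 96.7% | >99.9% | 96.7% |

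Overall power reaches 89.3% only at a true rate of about 24.6%.

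Changing the final cut-off does not recover the loss. With 19 of 125, two-stage power at 20% is 73.6% and the upper-tail error is 2.6%, just above 2.5%. While the Stage 1 rule stands, no final cut-off can take power above 76.6%.

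**The case against.** The best defence is that 11.4 contains no arithmetic slip. The sentence speaks of the sample size, the figure is exact for 125 participants with rejection at 20, and the paragraph before it discloses the 76.6%. A careful reader can see that there is about a 1 in 4 chance of stopping early. If Stage 2 does open, the chance of missing 20 responders at a true 20% is 6.7%, so 89.3% errs on the cautious side for reading a completed Phase 2. Safety is the primary objective, PSA response is a secondary endpoint, 11.1.1 calls the analyses mainly descriptive, and the stop lowers the type I error rather than raising it.

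Much of this stands. The 89.3% is correct as a fixed-sample figure, a completed negative Phase 2 is not misjudged in the harmful direction, and the descriptive setting limits the consequences. It does not rescue the statement. The fixed-sample reading describes a trial of 125 with no Stage 1 stop, which the protocol does not run. The reader is left to combine two probabilities that cannot simply be multiplied, because the 25 are part of the 125: 0.766 × 0.893 gives 68.4%, which is also wrong. And 11.4 does set out a null rate, a significance level, a power and a rejection rule, so the power it quotes should be the one the design has.

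SMC discretion does not help either. The stop wording gives no room to continue at 3 or fewer responders, and holding Stage 2 for safety reasons could only reduce power further.

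**Conclusion.** The concern holds. Under the rules in 4.1.2 and 11.4, overall power at a true 20% response rate is 71.5%, not 89.3%, a shortfall of 17.8 percentage points. Power conditional on Stage 2 opening is 93.3%. The overall upper-tail type I error at 10% is 1.5%.

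These figures assume independent participants, the same true response rate in both stages (including the 6 participants brought in from Phase 1), a full 100 in Stage 2 although the synopsis says up to 100, a Stage 1 stop applied as written, and no stop on safety grounds. The bound of 76.6% needs less: only that the Stage 1 rule is followed and the true rate in the first 25 is 20%.

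**What to change.** Keep the design and correct the statement in Protocol 11.4. Suggested text: *Allowing for the Stage 1 rule (at least 4 responders of 25), the overall power to reject a 10% response rate is 71.5% at a true rate of 20%, and 93.3% conditional on Stage 2 opening; the overall upper-tail type I error at 10% is 1.5%. These figures assume the same response rate in both stages, 100 participants in Stage 2 and no stop for safety.* If 89.3% is kept, label it as single-stage power that ignores the Stage 1 stop.

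Use the same figures in the Phase 2 SAP. The current SAP says that Phase 2 has not commenced and that its SAP is still to be written, so the correction can be made before the figure is carried forward.

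The cost is a sentence or two in each document and a less favourable stated power. It needs no additional participants and no change to either decision rule. If the sponsor finds 71.5% too low, that is a separate design question, and the final cut-off alone cannot resolve it.
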